Title page:

Title: Comparison of Clinical and Radiographic Success Between:
Mineral Trioxide Aggregate (MTA) & Ferric Sulfate (FS) Pulpotomies for Primary Molars.

NCT 02783911

Date: Sep 02, 2014

Comparison of Mineral Trioxide Aggregate and Ferric Sulfate:
Pulpal Medicaments for Pulpotomized Primary Teeth

Statistical analysis plan

The following clinical information were collected from the charts: Mobility, pain, abscess/draining fistula, and facial swelling. Exfoliation of the pulp treated teeth was recorded and graded as normal, early, or delayed based on the age of the patient at the time of the recall and on the exfoliation status of the contralateral tooth. If there is any clinical signs of the above the tooth will be count as clinical failure.

Data was analyzed using the Statistical Package for Social Sciences v 16.0 (SPSS Inc., Chicago, Ill). The difference between the materials was analyzed using chi-square, Significance level was set $P < .05$.

Chi-Square Tests

	Value	df	Asymptotic Significance (2- sided)	Exact Sig. (2- sided)	Exact Sig. (1- sided)
Pearson Chi-Square	.059 ^a	1	.808		
Continuity Correction ^b	.000	1	1.000		
Likelihood Ratio	.060	1	.807		
Fisher's Exact Test				1.000	.603
Linear-by-Linear Association	.057	1	.812		
N of Valid Cases	24				

a. 2 cells (50.0%) have expected count less than 5. The minimum expected count is 2.25.

b. Computed only for a 2x2 table

Summary: The result showed there is no statistical difference in long term clinical success between the two pulpotomy medicaments. (MTA vs FS)

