Title page:

Title: Comparison of Clinical and Radiographic Success Between:
Mineral Trioxide Aggregate (MTA) & Ferric Sulfate (FS) Pulpotomies for Primary
Molars.

NCT 02783911

Date: Sep 02, 2014

Statement of Problem

Premature loss of a tooth from caries or trauma can lead to malocclusion and/or to esthetic, phonetic, function problems, super eruption of the opposing tooth and costly procedures to correct and maintain space. A pulpotomy is one type of treatment for vital pulp therapy. The aim of the treatment is to preserve the radicular pulp, avoiding pain and swelling, to retain the tooth and preserve arch integrity.

Formocresol (FC) has a long history for pulpal medicament with a success rate of up to 97%. Its use, however, has been questioned due to published studies raising concerns for systemic distribution, carcinogenicity, mutagenicity, and immune sensitization. These concerns have led to the search and use of different materials and techniques to replace FC as a pulpal medicament that is cost effective, safe, and predictable. Calcium hydroxide, diluted formocresol, electrosurgery, lasers, ferric sulfate (FS), mineral trioxide aggregate (MTA), and sodium hypochlorite have been used as alternatives to FC for pulp therapy. Of these alternatives, MTA and FS have the most similar clinical and radiographic success as FC but the number of studies evaluating their success is limited in primary teeth. There has not been any study comparing MTA to FS for use in primary molar pulpotomies.

The purpose of this study is to evaluate which of these materials, gray MTA (GMTA) or FS, has the best long-term success rates with the least amount of adverse effects in primary molar pulpotomies. We will clinically and radiographically compare the success rates of MTA and ferric sulfate pulpotomies in primary teeth.

Review of Literature

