Follow-up appointments at 6 months, 9 months, and 12 months will be completed for subjects. The follow-up appointments will consist of a clinical examination and bite-wing view periapical radiographs to determine success(s)/failure(s) of two different pulpotomized teeth.

The criteria for a successful pulpotomy will include:

- retained for the length of the study or exfoliate naturally
- normal bone trabeculation in the periapical region
- no abscess or fistula
- contained internal resorption is acceptable
- calcific metamorphosis is acceptable

When the teeth exfoliate or require extraction, the teeth with pulpotomies will be collected and histologic slices will be completed to analyze for what types if any cellular changes from the use of the pulpal medicaments.

Statistical Analysis:

Data and statistical analysis will include descriptive and inferential statistics. Inferential statistical analysis will use SPSS 16 (SPSS, Chicago, IL) with a significance level set at $P \leq 0.05$

Budget:

Item	Units Needed	Price/Unit	Total Price
Patient incentive – follow-up visits	60	\$50	\$3000
Mineral Trioxide Aggregate	5 dose packets	\$475	\$475
Ferric Sulfate	1	\$35	\$35
3M Stainless steel crowns	60	\$5	\$300
Copying, stationery , paper, pen, 2 clip board			\$300.00
Total			\$4,110

Proposed Research Milestones:

Continuation of Established IRB#: 5140262

March 2016:

- Data collection

March 2016:

- Proposal preparation and submission for approval by the Research Guidance Committee

April 2016:

- Protocol preparation, submission, and approval by Loma Linda University School of Dentistry Research Committee

June 2016- June 2017:

- Data analysis and article preparation for review and submission

References:

- Casamassimo, P. S. (2013). Pediatric Dentistry Infancy Through Adolescence. St. Louis, Missouri, Elsevier Saunders.
- Chen, J. W. (2012). "Materials for primary tooth pulp treatment: the present and the future." Endodontic Topics 2012 **23**: 41-49.

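### The SAP analyses only clinical signs and exfoliation from the charts; as written, the radiographic half of the trial's stated comparison is never analysed

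*SAP*

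**What the plan says.** The title on both documents is "Comparison of Clinical and Radiographic Success Between" the two materials. The protocol's Statement of Problem sets the objective: "We will clinically and radiographically compare the success rates of MTA and ferric sulfate pulpotomies in primary teeth". Its Methods and Materials section plans visits at 6, 9 and 12 months and says: "The follow-up appointments will consist of a clinical examination and bite-wing view periapical radiographs", with the purpose of deciding success or failure. The list of criteria for a successful pulpotomy that follows includes "normal bone trabeculation in the periapical region", and adds that "contained internal resorption is acceptable" and that calcific metamorphosis is acceptable too.

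The SAP describes its data this way: "The following clinical information were collected from the charts: Mobility, pain, abscess/draining fistula, and facial swelling". It also records exfoliation as normal, early or delayed. Its only failure rule is "If there is any clinical signs of the above the tooth will be count as clinical failure". It names one chi-square comparison of the materials, prints one 2x2 table, and ends: "The result showed there is no statistical difference in long term clinical success between the two pulpotomy medicaments".

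**The concern.** The protocol makes the radiograph part of the outcome definition. A symptom-free tooth with abnormal periapical bone fails the protocol's criteria, but the SAP's rule does not count it as a failure. The SAP therefore estimates a different quantity from the one the protocol set out to compare.

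The clinical comparison is not biased as a comparison of clinical success, and the Summary labels it as clinical. But it does not answer the protocol's question. A reader of a document whose title names both kinds of success finds no radiographic result and no statement that it was not assessed.

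**Working it through.** **Step 1. Compare the two documents element by element.**

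| Element | Protocol | SAP |
|---|---|---|
| Stated comparison | Clinical and radiographic (title, objective) | Clinical and radiographic (title only) |
| Data | Clinical examination and radiographs at 6, 9 and 12 months | Four clinical signs from charts; exfoliation grade |
| Failure or success rule | Five-item list, including periapical bone | Clinical failure only |
| Test | Descriptive and inferential statistics, endpoint not named | One chi-square |
| Conclusion | Not applicable | Clinical success only |

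By my reading, the protocol's five items comprise one explicit radiographic requirement (periapical trabeculation), two permissive items (contained internal resorption, calcific metamorphosis) and two clinical items (retention or natural exfoliation; no abscess or fistula). The word "contained" implies that uncontained resorption fails, so the radiographic content may be larger than one item. The protocol's Statistical Analysis paragraph names no endpoint, so it does not fill the gap.

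**Step 2. Reproduce the SAP's only result.** Inputs from its Chi-Square Tests table: N = 24, Pearson .059, minimum expected count 2.25, two cells with expected count below 5.

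- The minimum expected count is the product of the two smaller margins divided by N, so that product is 2.25 × 24 = 54. With neither margin above 12, the only pair is 6 and 9. The margins are 9/15 and 6/18.
- Among tables with these margins, only cells 2, 7, 4, 11 give the printed Pearson value: (2×11 − 7×4)² × 24 / (9 × 15 × 6 × 18) = 864 / 14,580 = .0593, p = .808.
- The same table gives likelihood ratio .060, continuity-corrected .000, linear-by-linear .057, Fisher two-sided 1.000 and one-sided .603. All match the SAP.

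The printed output is therefore one binary outcome on 24 cases. The SAP prints no second, radiographic table.

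**Step 3. Ask how far radiographic failures could move the verdict (illustration only).** The margins are unlabelled. If failures are the smaller outcome column, the arms are either 2/9 vs 4/15 or 2/6 vs 7/18. Reclassify k clinical successes in one arm as radiographic failures and recompute Fisher's two-sided p.

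| k added to the smaller arm | 2/9 vs 4/15 | 2/6 vs 7/18 |
|---|---|---|
| 1 | 1.00 | .67 |
| 2 | .41 | .36 |
| 3 | .21 | .155 |
| 4 | .092 | .016 (6/6 vs 7/18) |
| 5 | .033 (7/9 vs 4/15) | not possible |

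Added to the larger arm, p falls below .05 only at 7 (15-tooth arm, p = .033) or 8 (18-tooth arm, p = .038). If failures are instead the larger column (7/9 vs 11/15, or 4/6 vs 11/18), no number added to one arm gives p < .05; the lowest values are .13 and .054.

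**The case against.** The strongest defence is that the Summary claims only clinical success, so no false radiographic claim is made, and that the verdict may well not change. Both statements are true. Neither supplies the analysis that the title and objective promise, and the point does not rest on a reversed p-value.

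A second defence is that the documents do not prove that films went unread. The protocol's general statistical wording does not exclude a radiographic analysis, and the SAP's table does not label its outcome. This stands as a limit: that the table shows clinical failure is inferred from the failure rule and the Summary, and the finding concerns the plan as written. But the SAP text runs from variables to conclusion with no sign of removed material, and nowhere specifies a radiographic analysis.

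The illustration in Step 3 is rightly called weak. It assumes which column is failures and puts every hidden failure in one arm. It shows only that the verdict need not move.

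There are also practical objections to the remedy. Naturally exfoliated teeth may have no 12-month film. The protocol's list already counts them as successes for overall success, and reporting readable films per arm shows the denominator for the radiographic result. Simple intervals assume independent teeth, and neither document states one tooth per child; the budget's 60 follow-up incentives and 60 crowns are consistent with it. Finally, scheduled films may not have been taken, so the fix needs a fallback.

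**Conclusion.** The concern holds. Three radiographic visits are scheduled and the SAP describes an analysis of none of them. Half of the stated objective has no planned test, and success as the protocol defines it is not reported. This goes beyond missing detail, because the SAP's endpoint cannot register a failure seen only on film.

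The size of the effect on the results is unknown and cannot be computed from these documents. The conclusion rests on the text of the two documents, not on the illustration, and does not assume that films were missing or unread. Confidence is high.

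**What to change.** Add two comparisons to the SAP, both at 12 months, the protocol's last visit:

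1. Radiographic success by arm.
2. Overall success by arm under the protocol's full list of criteria, clinical and radiographic.

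Give each a risk difference with a Newcombe 95% confidence interval. Read the scheduled films without knowledge of arm where possible. Before reading, write down how "contained" internal resorption is judged. Report the number of readable films per arm. Keep the clinical-only result alongside, and state that both comparisons were added after the clinical result was known, to restore the protocol's definition.

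If the films were not taken or not read, reword the Summary to say that radiographic success was not assessed and that the conclusion covers clinical success only.

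The cost is SAP wording, film reading and two more 2x2 tables. No visits are added to the protocol's schedule. The drawbacks are that some films may be missing or unreadable, the added analyses are post hoc, and reported success rates may fall. The fallback costs one sentence.

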- 9) MTA is a biocompatible material and its sealing ability is better than that of amalgam or zinc oxide-eugenol. It is a powder that sets in the presence of moisture with a pH of 12.5. The setting time of the cement is 4 hours and its compressive strength is 70 MPA, which is comparable with that of IRM (Torabinejad, M., 1999).

Methods and Materials

Children between the ages of 4-9, with first or second primary molars with normal or reversible pulpitis that have vital carious pulp exposures due to caries and pulps that bleed when entering the pulp chamber. No clinical symptoms or evidence of pulp degeneration, such as excessive bleeding from the root canal, history of swelling, mobility, or sinus tract. No radiographic signs of internal or external root resorption, inter-radicular and/or periapical bone destruction, or furcation radiolucency. No more than one third physiologic root resorption has occurred. Teeth that will be retained for 12 months after the pulpotomy procedure and stainless steel crown restoration, will be asked to participate in this study. Children can be ASA I or II that have cooperative behavior that will enable follow-up appointments for examinations and radiographs. Children meeting the criteria for this study will be treated at Loma Linda University's Pediatric Dental Clinic, LLU Children's Hospital with general anesthesia, or Koppel Special Care Dentistry Center at LLU.

Prior to pulpotomy treatment, the subjects will be randomly assigned into two groups: 1) MTA pulpotomy with stainless steel crown or 2) ferric sulfate with stainless steel crown. Operators involved will draw blindly into a box that has 60 papers: 30 marked MTA and 30 marked FS. The teeth will be anesthetized using 2% lidocaine with (1:100Kepi). The tooth will be isolated using a rubber dam. A new slow-speed #6 or #8 round bur will be used to remove caries. A new #330 carbide bur and a high speed will be used to access pulp chamber. Hemostasis will be achieved with direct pressure from a sterile cotton pellet moistened with sterile water. MTA or FS (whichever randomly assigned) will be placed onto pulpal stumps. ZOE B&T mixture will be placed into pulp

chambers. Molar will be immediately restored with a stainless steel crown cemented with Ketac-Cem Liquid. A post procedure bitewing radiograph, that shows the subject's tooth furcation and complete root, will be taken.

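### The SAP concludes on the two materials from 24 cases against a planned 60, with no account of the difference; the result is inconclusive and should be stated as such

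*SAP*

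**What the plan says.** Protocol, Methods and Materials: "the subjects will be randomly assigned into two groups", and the mechanism is "Operators involved will draw blindly into a box that has 60 papers: 30 marked MTA and 30 marked FS". On follow-up: "Follow-up appointments at 6 months, 9 months, and 12 months will be completed for subjects". The Budget table gives 60 units for "3M Stainless steel crowns" and 60 for the follow-up incentive, so 60 is the intended size throughout the protocol.

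SAP: clinical signs were taken from charts, and if any listed sign is present "the tooth will be count as clinical failure". The Chi-Square Tests table gives "N of Valid Cases" = 24, Pearson chi-square .059 (p = .808), likelihood ratio .060, Fisher 1.000 two-sided and .603 one-sided, and linear-by-linear .057. Its footnote reads "2 cells (50.0%) have expected count less than 5. The minimum expected count is 2.25". The crosstabulation itself is not printed. The Summary then states: "The result showed there is no statistical difference in long term clinical success between the two pulpotomy medicaments".

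Neither document gives the numbers drawn, treated, followed or lost. Neither names an analysis population, a rule for missing outcomes or the visit analysed.

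**The concern.** The sole inferential result rests on 24 cases where the design provides for 60, and nothing explains the gap. The explanation determines what the result means. If recruitment stopped early, the comparison is randomised but very small. If children were randomised and then not seen, and return depends on how the tooth fared, the protection of randomisation may be lost. Incomplete charts, exclusions, or restriction to one recall visit would each raise a different question.

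The Summary draws one conclusion about the two materials regardless of which applies. A reader will take it as the answer from the planned trial, and probably as evidence that the materials perform alike.

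**Working it through.** **Inputs.** From the SAP table: N = 24, minimum expected count 2.25, two cells below 5, chi-square .059. From the protocol: 60 slips, 30:30.

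**Step 1: recover the margins.** Minimum expected count = r × c / N, where r and c are the smaller row and column totals. So r × c = 2.25 × 24 = 54. Each is at most 12, and the only such factor pair is 6 × 9. The margins are 6/18 and 9/15. The expected counts are 2.25, 3.75, 6.75 and 11.25, two of them below 5, as printed.

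**Step 2: recover the cells.** Let x be the count where the margins 6 and 9 meet. Chi-square = 24 × (24x − 54)² / (6 × 18 × 9 × 15) = 24 × (24x − 54)² / 14580.

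| x | chi-square |
|---|---|
| 0 | 4.80 |
| 1 | 1.48 |
| 2 | 0.059 |
| 3 | 0.53 |
| 4 | 2.90 |
| 5 | 7.17 |
| 6 | 13.33 |

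Only x = 2 fits, so the cells are 2, 7 / 4, 11.

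**Step 3: reproduce the rest of the printed table.** Pearson .0593 (p = .808). Likelihood ratio .0599 (p = .807). Fisher 1.000 and .603. Linear-by-linear .0593 × 23/24 = .0568 (p = .812). The continuity-corrected value is 0, because |2 × 11 − 7 × 4| = 6 is less than N/2 = 12. Every printed figure is matched.

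**Step 4: the two readings.** These assume that the table is material by clinical success and that the rarer outcome is failure. Which material has the smaller arm cannot be recovered.
- Reading A, arms 9 v 15: failures 2/9 (22.2%) v 4/15 (26.7%), difference −4.4 points.
- Reading B, arms 6 v 18: failures 2/6 (33.3%) v 7/18 (38.9%), difference −5.6 points.

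**Step 5: 95% intervals (Newcombe).** Lower = d − √[(p1 − l1)² + (u2 − p2)²]; upper = d + √[(u1 − p1)² + (p2 − l2)²], where l and u are Wilson limits.
- A: Wilson limits 0.063 to 0.547 and 0.109 to 0.520. Interval −34 to +32 points.
- B: Wilson limits 0.097 to 0.700 and 0.203 to 0.614. Interval −38 to +36 points.

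**Step 6: could the split be chance?** For 24 taken at random from 30 + 30 without replacement, twice the lower hypergeometric tail is 2 × 0.0936 = 0.19 for 9 or fewer in the smaller arm, and 2 × 0.00166 = 0.003 for 6 or fewer. Fisher's test of 9/30 v 15/30 or 6/30 v 18/30 retained gives the same two p-values, so they apply whether drawing stopped at 24 or follow-up was lost from 30:30.

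**Step 7: extreme-case bounds.** These apply only if all 60 slips were drawn and one tooth was counted per subject, leaving 60 − 24 = 36 (60%) without an outcome.
- A, 21 and 15 missing: 2/30 − 19/30 = −56.7 points; 23/30 − 4/30 = +63.3 points.
- B, 24 and 12 missing: 2/30 − 19/30 = −56.7 points; 26/30 − 7/30 = +63.3 points.

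If the rarer outcome is success instead, the intervals and bounds change sign and keep their widths.

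**The case against.** The strongest reply is that nothing shows that anyone was dropped. The documents establish that 60 slips were prepared and 60 sets of materials budgeted, not that 60 were drawn. SPSS prints its valid-cases row whether or not data are missing. If 24 were drawn and all have outcomes, there is no attrition and no bounds are needed. This stands. A reader might infer that the SAP discarded 36 randomised children and analysed a selected subset, but the documents do not support that.

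A reader might also infer that unequal arms invalidate the test. They do not: imbalance alone costs power and introduces no bias. The 9 v 15 split is within chance, and the output cannot show which split is the true one. That stands too.

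The units may also differ. Subjects are randomised while teeth are counted, so 24 against 60 may not compare like with like. This limits any attrition percentage, and it is a further reason to state the unit.

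On early failures, the SAP counts any listed clinical sign as failure without tying it to one visit, and the protocol's success criteria require retention or natural exfoliation. The event is therefore partly covered. What is not explicit is that a failure charted early is kept when the child has no later visit.

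Finally, the Summary's wording literally describes p = .808. That is true, but it is offered as the conclusion on the two materials, with no estimate, interval or caveat.

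**Conclusion.** The point holds as a fault in accounting and in the conclusion drawn. The analysed size is 24 against a planned 60, the shortfall is unexplained, and the Summary's statement on long-term clinical success is not supported for the planned 60. Even taken alone, the 24 cases leave differences of roughly a third in either direction open: about −34 to +32 points, or −38 to +36.

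The reconstructed cells are certain given the printed statistics. Treating them as material by clinical success follows from the Summary; treating the rarer outcome as failure is an assumption. The bounds of −57 to +63 points depend on all 60 slips having been drawn with one tooth per subject.

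Selective loss remains a risk that the documents neither show nor exclude. Under-recruitment, loss to follow-up, incomplete charts and exclusions all remain possible. Only a 6 v 18 split would itself be evidence of something beyond chance.

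**What to change.** In the SAP:

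1. Restate the analysed size as 24 of [n] randomised. Give a per-arm disposition (drawn, treated, seen at 6, 9 and 12 months, extracted, withdrawn, lost, with reasons), the unit counted, and the visit analysed.
2. Analyse every randomised case in the arm drawn, and state explicitly that a failure charted at any visit is carried forward.
3. Print the 2x2 table and the risk difference with its 95% CI. If any randomised case has no outcome, add best-case and worst-case bounds.
4. Reword the Summary as inconclusive among the 24 cases analysed, not as evidence that the materials perform alike.

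The cost is one disposition table, one short sensitivity table and some rewording, drawn from the charts and whatever allocation record was kept. The protocol does not mention an allocation log; if none exists, the SAP should say so. The downside is a less favourable stated conclusion.

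### The SAP already contains its result and uses a clinical-only failure rule that differs from the protocol's success criteria, so that rule cannot be shown to be prespecified

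*SAP*

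**What the plan says.** **Dates.** Both title pages read "Date: Sep 02, 2014". The protocol (Methods and Materials) puts enrolment in the future: "Prior to pulpotomy treatment, the subjects will be randomly assigned into two groups". It then sets the visits: "Follow-up appointments at 6 months, 9 months, and 12 months will be completed for subjects". Each visit is to include a clinical examination and radiographs. The protocol's Proposed Research Milestones open with "Continuation of Established IRB#: 5140262" and list data collection in March 2016. April 2016 has "Protocol preparation, submission, and approval by Loma Linda University School of Dentistry Research Committee", and June 2016 to June 2017 has "Data analysis and article preparation for review and submission".

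**Protocol outcome.** The success criteria are retention or natural exfoliation, normal periapical bone trabeculation, and "no abscess or fistula". Contained internal resorption and calcific metamorphosis are tolerated.

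**SAP outcome.** Mobility, pain, abscess or draining fistula, and facial swelling were taken from charts. Exfoliation was graded as normal, early or delayed. Any clinical sign among the items listed makes the tooth a clinical failure. No radiographic criterion appears, although the title still promises clinical and radiographic success.

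**SAP result.** The SAP prints the test output for 24 valid cases and closes with "Summary: The result showed there is no statistical difference in long term clinical success between the two pulpotomy medicaments".

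**The concern.** An analysis plan protects a trial by fixing the outcome before the data can influence it. Here the only statement of the outcome rule that was tested sits in the same document as the test's result, under a date on which the protocol was still describing enrolment as future. The rule is also not the one in the protocol. A reader of the Summary is told neither that the radiographic half of the question is missing nor that the clinical half was scored on a different list of signs.

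Nothing else in the documents anchors the choice. The protocol's Statistical Analysis section names no test and no primary visit; it promises only descriptive and inferential statistics. At stake is whether the conclusion can be read as the answer to the question the protocol posed.

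**Working it through.** **1. Reproduce the SAP's output.** The inputs are N = 24, minimum expected count 2.25 and Pearson chi-square .059. A search over all 2x2 tables leaves only tables with margins 6/18 and 9/15, for example 2/9 against 4/15:

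- Minimum expected count: 9 × 6 / 24 = 2.25. The next smallest is 15 × 6 / 24 = 3.75. The other two are 6.75 and 11.25, so two cells are below 5, as the footnote says.
- Pearson: 24 × (2 × 11 − 7 × 4)² / (9 × 15 × 6 × 18) = 864 / 14,580 = 0.0593, p = .808.
- Likelihood ratio 0.060 (p = .807); continuity-corrected 0.000 (p = 1.000); linear-by-linear 0.0593 × 23/24 = 0.057 (p = .812); Fisher 1.000 two-sided and .603 one-sided.

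Every printed figure is matched, so this is a finished analysis and not a template. The table 2/6 against 7/18 gives the same output. The SAP does not say which margin is the treatment and which is the outcome. If each case corresponds to one randomisation paper, 24 of the 60 planned is 24/60 = 40%.

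**2. Set the date against the schedule.** Assume that the title-page date is taken at face value and that no tooth was treated earlier. The earliest visits are then:

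- 6 months: 2 March 2015
- 9 months: 2 June 2015
- 12 months: 2 September 2015

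The data-collection milestone, March 2016, is about 18 months after the title-page date (546 days to 1 March 2016).

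**3. Compare the two rules.**

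| Item | Protocol criteria | SAP failure rule |
|---|---|---|
| Abscess or fistula | must be absent | failure |
| Exfoliation | natural exfoliation allowed | graded; unclear whether early or delayed is a failure |
| Periapical trabeculation | must be normal | absent |
| Internal resorption, calcific metamorphosis | tolerated | absent |
| Mobility, pain, facial swelling | not listed | failure |

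**4. Apply both rules to the same tooth.**

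- Abnormal periapical bone, no clinical sign: fails the protocol criteria; not a failure under the SAP.
- Pain, mobility or facial swelling in a retained tooth with normal bone and no abscess or fistula: meets every listed protocol criterion; a failure under the SAP.
- Early or delayed exfoliation without another sign: depends on what the protocol means by natural and on how far back the SAP's failure sentence reaches. Neither is stated.

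Disagreement is therefore possible in both directions. The documents give no counts by criterion and no radiographic findings, so its effect on p = .808 cannot be calculated.

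**The case against.** The strongest reply is that little of this shows the rule was changed after the data were seen. Much of that reply stands.

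- **The date is weak evidence.** The protocol has the same date yet lists 2016–2017 milestones and continues an established ethics number. The date may not be when either text was written.
- **The SAP is openly retrospective.** It is written mostly in the past tense and never claims to have been prespecified.
- **The SAP's signs are not foreign to the protocol.** The protocol names avoiding pain and swelling as an aim, screens for swelling and mobility at entry, and schedules clinical examinations. It also introduces its list as what the criteria will include, which need not be exhaustive. This weakens the second example in the working. It does not touch the first: a listed criterion that is not met is a failure however many others exist.
- **Two of the listed protocol items are tolerances.** A clinical failure rule has nothing to carry over from them, and exfoliation does reappear in graded form.

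A reader might infer that the rule was chosen post hoc to obtain this result. The documents do not show when it was chosen, and the failure sentence itself is in the future tense. A reader might also infer that the study began before approval, because data collection (March 2016) precedes the April 2016 item. That item is approval by a school research committee, under an ethics number described as already established, so the order does not prove it. Nor does an inflated false-positive rate fit: the reported result is null and no positive claim is made.

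None of this restores the SAP as evidence of prespecification, and none of it supplies the missing radiographic criterion.

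**Conclusion.** The point holds in a limited form and should be corrected. The document headed as an analysis plan contains the completed test and the conclusion, so it cannot show that its outcome rule was set beforehand. Its date is either wrong or incompatible with the protocol's follow-up schedule. The second alternative assumes that no child was treated before 2 September 2014. The need for correction does not depend on which alternative is true.

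The substantive difference is the loss of the radiographic criterion. With mobility, pain and facial swelling added and the status of early or delayed exfoliation left open, the two rules can classify the same tooth differently. The reported test answers at most the clinical half of the question in the title.

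It does not follow that the two rules give different success rates in these teeth, or that the conclusion would change. They may differ; the documents allow no stronger statement.

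**What to change.** 1. Give the SAP its true date. State that it was completed with the results in hand and that its outcome rule is not shown to be prespecified.
2. Report success by the protocol's criteria, including periapical trabeculation, as the protocol-defined outcome for all teeth with the scheduled radiographs. State how many lack them. Because the protocol names no primary visit, state which visit each figure refers to.
3. Present the SAP's any-sign rule as a separate clinical outcome. State whether early or delayed exfoliation counts as failure, and add a cross-table of teeth that the two rules classify differently.
4. Limit the Summary to charted clinical signs in 24 cases.

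**Cost.** Wording, one cross-table and some extra tabulation. The second step depends on the scheduled radiographs having been taken and kept, which the documents do not confirm. The conclusion becomes weaker.
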